2.2 Aims

Healthcare technology assessment is the multidisciplinary evaluation of medical technologies with regard to **feasibility, safety, efficacy**, indications for use, cost, and cost-effectiveness. A complete assessment should explore the scientific, ethical, economic, and social reasons for adopting a technology and it may influence the quality of service and distribution of resources.

In this multicenter study, we aim to assess the first 3 important criteria.

Aim 1 – To determine the **feasibility** of using a wireless system immediately after delivery and for the first 2h of age, while in the obstetrical center under unsupervised parents' care. The following outcomes will be measured for both wired and wireless systems:

- a. Percentage of time for which HR, RR, SpO₂ and T_{skin} data are displayed.
- b. Occurrence of gaps in signal detection/recordings (% and length).
- c. Causes of the gaps in signal detection/recordings.
- d. Descriptive analysis of user surveys and their satisfaction with the wireless system.

Aim 2 - To investigate the **safety** of using this wireless system immediately after delivery and for the first 2h of age. The following outcomes will be measured for both wired and wireless systems:

- a. Skin score to be determined by a blinded dermatologist using de-identified pictures of the skin after removal of the sensors of each system.
- b. Pain scale to assess any discomfort or pain during the removal of the sensors.
- c. Clinically significant events detected by the wired system (HR < 100 bpm or SpO₂ < 80%) but missed by the wireless system.

Aim 3 – To assess the **accuracy** of this wireless system in measuring HR, RR, SpO₂ and T_{skin} signals compared with the “standard of care” wired system. The following outcomes will be computed:

- a. Correlation coefficient
- b. Slope
- c. Variance accounted for
- d. Bias

Further subgroup analyses will be conducted to assess for systematic differences in feasibility, safety, and accuracy of the wireless system between the following:

- High vs. Low and Middle income countries
- Female vs. Male subjects
- Term vs. Preterm (born < 37 weeks gestational age) infants
- C-section vs. Vaginal delivery

- Skin pigmentation

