3.3.3 Study Interventions

Each newborn enrolled in the Study will be monitored simultaneously by both the standard of care (control) wired vital sign monitoring system (Infinity M540 monitor, Draeger, Germany) and the wireless monitoring system (intervention) (ANNE Arc chest sensor, SIBEL Health, Illinois, USA and Limb sensor (RAD7, Masimo) (Figure 9).

Both monitoring systems, will simultaneous record heart rate, respiratory rate, oxygen saturation, and skin temperature for the first 2h of age.

Figure 9. Monitoring systems – ECG and temperature

Figure 10. Monitoring Systems – SpO2

All materials and equipment required for the conduct of the study will be provided to the participating sites by the lead site. All research team members at all sites will be trained on the placement and removal of the wireless and wired monitoring including appropriate cleaning and disinfecting protocols. Training on the use of the BioDash system will also be provided as part of the study training at all sites.

Vital Sign Monitoring:

If a baby is born via:

1. *Vaginal Delivery:* Following normal, vaginal delivery, the wireless skin sensor monitoring system (Anne Arc & RAD7 Limb,Sibel Health Inc - Masimo) will be immediately placed on the newborn. In order to promote the standard practice of bonding between newborn and mother the standard of care wired monitoring system (Infinity Monitor, Drager) will be placed on the newborn after 10-20 min of age.
2. *C-section:* Immediately before birth, the infant will be randomized for the type of monitoring system to be applied first: a) the wireless sensors (Anne Arc & RAD7 Limb,Sibel Health Inc - Masimo) or b) standard of care wired system (Infinity Monitor, Drager). In order to promote the standard practice of bonding between newborn and mother the second monitoring system will be placed on the newborn after 10-20 min of age.

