- Skin Pigment: Previous research has highlighted the challenges of some pulse oximeters in providing accurate readings for skin with darker pigmentation and as a result has emphasized the need to investigate the performance of pulse oximeters for different skin tones^{38,39}. The infant's skin color will be recorded using the adapted Munsell System Soil Color Chart (2009 Revision, Munsell Color, Grand Rapids, Michigan), Hue7.5YR to investigate impact of skin pigmentation on pulse oximetry accuracy. This scale has previously been used in research on neonates⁴⁰.
- *Pain Assessment*: As well, neonatal pain will be assessed throughout the sensor removal process. The pain scale (NIPS) will be completed by the study team member at the time of sensor removal and entered into REDCAP.
 - Neonatal Infant Pain Scale (NIPS)³⁶ : At the time of device removal, the researcher will complete the NIPS to ensure removal of adhesive does not cause significant discomfort to the patient. The scale consists of 6 items. Scores range from 0 to 7, with scores greater than 3 indicating presence of pain. This scale has been widely validated for the assessment of acute pain in neonates. This scale will be included in the Data Collection Form.
- *Surveys*: In order to assess feasibility on the use of wireless sensors to monitor babies after birth, a survey will be conducted to get the opinions of parents and Health Care Professionals involved in the care of the baby and mother. The survey will be presented in hard copy form as well as through REDCAP.
 - Parent Survey: Parents of the participating infant will be asked to complete a short survey to after the sensors of both systems are removed. The survey will be coded with the study code assigned to the participating infant, no personal health information or personal information will be asked of the parent for the completion of the survey. (See Appendix 2).
 - Health Care Professional Survey: HCPs involved in the care of the infant and mother after birth will be asked to complete a short survey after the sensors of both systems are removed in order to assess how the HCPs felt about the wireless skin sensors as compared to their experience of the standard of care wired monitoring system. (See Appendix 2).

REDCAP

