Clinical data, images, information as described in the Data Collection Form (Appendix 1) and Survey (Appendix 2) responses will be entered into a REDCAP database hosted at the RI-MUHC through the CORD platform. A service agreement has been entered into with CORD and the Principal Investigator for the REDCAP database set up and support for the study's data management. Each participating site will be provided access to the study REDCAP database at the RI-MUHC and be responsible for entering their site's

data into REDCAP. Participating sites will be expected to sign a site user agreement before permitting access to REDCAP. The HCP and parents will be provided a link to the survey in REDCAP or a hard copy depending on their preference and/or the preference of each participating site. The sites will be asked to send their a copy of each completed Data Collection Form and a hard copy of the survey in order to query and ensure compliance and consistency in the conduct of data collection and data entry on a monthly basis. No site will be able to access another site's individual site data and will only have access to REDCAP for their site. The de-identified study database will only be accessible to the lead site and all analysis of the study data collected in REDCAP will be done by RI-MUHC study team members. Results will be shared with the participating sites on an ongoing basis for training purposes as well as to support the drafting and submission of manuscripts, abstracts, and presentations as the study progresses.

BIODASH

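### Aim 2b promises removal pain for each system, but the pain section of the Data Collection Form holds one NIPS total with no system label, removal order or time

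*Combined protocol and SAP*

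**What the plan says.** Section 2.2 opens the Aim 2 outcome list with "The following outcomes will be measured for both wired and wireless systems". Item b on that list is "Pain scale to assess any discomfort or pain during the removal of the sensors". The same section plans subgroup analyses of "systematic differences in feasibility, safety, and accuracy of the wireless system".

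Section 3.3.3 has both systems on the same infant: "Each newborn enrolled in the Study will be monitored simultaneously by both the standard of care (control) wired vital sign monitoring system", alongside the wireless one.

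Section 3.3.4 gives the pain instruction: "The pain scale (NIPS) will be completed by the study team member at the time of sensor removal and entered into REDCAP". It states the purpose as "to ensure removal of adhesive does not cause significant discomfort to the patient", treats a score above 3 as pain, and adds "This scale will be included in the Data Collection Form". It names no system, number of scores or removal order. On data entry it says that "information as described in the Data Collection Form (Appendix 1) and Survey (Appendix 2) responses will be entered into a REDCAP database".

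Section 5.1 makes pain scores one of the safety inputs reviewed after 200 and 400 patients. It expects discomfort to be negligible and has any evidence of it recorded and reported to the local and lead investigators. Section 4 describes no analysis of pain.

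**The concern.** Because each infant is its own control, a pain score says something about the wireless adhesive only if it is known which system was coming off when it was taken. Aim 2 states a by-system outcome. Neither the instruction to staff nor the form's pain section asks for the information that outcome needs.

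This matters in three places:

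- the final report on Aim 2b;
- the two safety reviews, where scores above 3 could reflect the new adhesive or the standard electrodes;
- the planned subgroup analyses of wireless safety.

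NIPS is a behavioural score taken at the moment of removal. A score that is not taken then, or not labelled, cannot be reconstructed later.

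**Working it through.** The plan gives no sample size, precision or expected rate for pain, so there is no figure of its own to reproduce. The check sets the stated outcome beside the means of recording it.

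**Step 1. What the outcome needs.** Two systems per infant (section 3.3.3) and an outcome for each (section 2.2) require two NIPS scores per infant, each labelled by system.

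**Step 2. What the pain section holds.** Appendix 1, section 2 has six items and one total. The item maxima are 1 + 2 + 1 + 1 + 1 + 1 = 7, which agrees with the 0 to 7 range in section 3.3.4, so the block is one complete NIPS. It has no field for system, removal order or time. The copy of the scale in Appendix 4 adds none.

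**Step 3. Whether another part of the form supplies the link.**

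| Appendix 1 | What it records | Ties a NIPS score to a system? |
|---|---|---|
| Opening lines | Overall start and end time | No |
| Section 3 | Order in which monitoring was applied | No; this is not removal order |
| Sections 5 and 6 | Timed comments; system-specific codes for sensors taken off and put back | No; the NIPS block has no time to match to them |
| Section 4 | Heart rate, respiratory rate and SpO2, wired and wireless rows | Split by system, but not pain |
| Section 8 | Skin events and skin score, wired and wireless blocks | Split by system, but no pain item |

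The form separates the systems for vital signs and skin, so the single pain block looks like an oversight.

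**Step 4. Consequence if completed as printed.** There is one unlabelled total per infant where two labelled ones are needed. Of 600 planned infants, 0 would have a score attributable to wired or wireless removal.

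**Step 5. When one score is enough.** Assume that a removal which would score above 3 on its own also takes the single total above 3. The rate for either system then cannot exceed the rate for the single total. With no infant above 3 among n, the one-sided 95% upper limit is 1 − 0.05^(1/n):

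- n = 200: 1.49%
- n = 400: 0.75%
- n = 576: 0.52%

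Here 576 = 600 × 0.96. It borrows the 4% drop-out in section 4, which comes from missing signal recordings and not from missing pain scores. The limits treat infants as independent and ignore clustering by site.

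**Step 6. What two labelled scores would give (illustration).** Let d be the share of infants above 3 on one system only. The documents give no value, so d = 5%, 10% and 20% are assumed. With 576 pairs and discordance split evenly, the 95% half-width for the paired difference is 1.96 × √(d/576), or 1.8, 2.6 and 3.7 percentage points.

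**The case against.** The strongest reply is that this is unstated operational detail and not a contradiction. Scoring at sensor removal is compatible with scoring at each removal, and nothing limits staff to one score per infant. Teams are trained on removing both systems, and neither the training material nor the REDCap screens are shown. A column could also be missing from the copy of the form read here, and Appendix 4, being the generic instrument, says little about the form's layout. This stands as a limit: the finding is conditional on the form being used as printed. It does not remove the gap. Section 3.3.4 makes the form the source for REDCap, nothing calls for a second entry, and a block filled in twice would still be unlabelled.

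A second reply is that discomfort is expected to be negligible, no pain test is planned, and section 3.3.4 wants only a check for significant discomfort. One score does serve that purpose, and Step 5 shows how well if scores above 3 do not occur. It does not serve the outcome as Aim 2 words it.

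A third reply is that section 5.1 has discomfort at removal recorded and reported separately. That may identify the system in individual cases, but it does not require attribution.

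A reader might infer that the whole form lacks system, order and time fields. It does not; only the pain section does. A reader might also infer that the safety reviews could not recognise a wireless problem at all. The documents do not support that either, given the separate reporting and the skin scores split by system.

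**Conclusion.** The point holds in conditional form. If Appendix 1, section 2 is completed as printed, and unless REDCap adds labelled entries, the by-system pain outcome in Aim 2b cannot be reported. Scores above 3 at the 200 and 400 reviews could not be assigned to a system from the score itself, and the wireless-specific pain subgroups fail for the same reason.

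In size, this is one unlabelled total where two labelled ones are needed, for every infant. The practical effect depends on how often scores exceed 3, for which the documents give no rate. If they are essentially absent, the single score is sufficient. If they are not, attribution is lost and enrolling more infants does not restore it.

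It is tempting to go further and attach a numerical range to the unknown wireless-minus-wired difference. That would only restate an assumed pain rate. It would also need the single total to exceed 3 exactly when at least one removal would, which is doubtful because distress can build up across both removals. No such range is claimed here.

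This should be corrected, since missed scores cannot be recovered. It does not affect the coverage or accuracy outcomes.

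**What to change.** In section 3.3.4, Appendix 1 section 2 and REDCap, require one NIPS labelled wired and one labelled wireless, each scored at that system's own removal, and record which system was removed first. If the existing REDCap build already does this, amend the text and the printed form to match.

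The cost is a second six-item block and one removal-order field, with no extra staff. Removal takes slightly longer. The scorer still knows which system is coming off, and distress from the first removal may carry into the second score, so two scores improve attribution without guaranteeing it. Alternating the removal order would help with carry-over but is optional.

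Fallback: reword Aim 2b as pain on removal of both systems together, and make no by-system pain claim at the reviews, in subgroups or in the final report. This is a short wording change, but it gives up the by-system pain outcome.

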2. PAIN ASSESSMENT

Score:

Facial Expression	
0 – Relaxed muscles	Restful face, neutral expression
1 – Grimace	Tight facial muscles, furrowed brow, chin, jaw, (negative facial expression – nose, mouth, brow)
Cry	
0 – No cry	Quiet, not crying
1 - Whimper	Mild moaning, intermittent
2 – Vigorous Cry	Loud scream; rising, shrill, continuous (Note: silent cry may be scored if baby is intubated as evidenced by obvious mouth and facial movement.)
Breathing Patterns	
0 – Relaxed	Usual pattern for this infant
1 – Change in Breathing	Indrawing, irregular, faster than usual, gagging, breath holding
Arms	
0 – Relaxed/Restrained	No muscular rigidity, occasional random movements of arms
1 – Flexed/Extended	Tense, straight legs; rigid and/or rapid extension/flexion
Legs	
0 – Relaxed/Restrained	No muscular rigidity, occasional random movements of legs
1 – Flexed/Extended	Tense, straight legs; rigid and/or rapid extension/flexion

State of Arousal	
0 – Sleeping/Awake	Quiet, peaceful, sleeping, or alert random leg movement
1 – Fussy	Alert, restless, thrashing
TOTAL	

***R**=Royal Victoria Hospital; **U** = UNICAMP; **B** = Uberlandia; **S** = Sanatorio Trinidad Palermo Hospital; **M** = Mbuya Nehanda Hospital (Harare, Zimbabwe); **N** = Neocare Baby Hospital (Harare, Zimbabwe); **C** = Maputo Central Hospital (Mozambique); **T** = Hospital Sanatorio Trinidad Palermo; **V** = Hospital Ramos Mejía; **H** = Hospital of Newborn Medicine (Buenos Aires, Argentina)

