0 – No Cry	Quiet, not crying	
1 – Whimper	Mild moaning, intermittent	
2 – Vigorous Cry	Loud scream; rising, shrill, continuous (Note: Silent cry may be scored if baby is intubated as evidenced by obvious mouth and facial movement.	
Breathing Patterns		
0 – Relaxed	Usual pattern for this infant	
1 – Change in Breathing	Indrawing, irregular, faster than usual; gagging; breath holding	
Arms		
0 – Relaxed/Restrained	No muscular rigidity; occasional random movements of arms	
1 – Flexed/Extended	Tense, straight legs; rigid and/or rapid extension, flexion	
Legs		
0 – Relaxed/Restrained	No muscular rigidity; occasional random leg movement	
1 – Flexed/Extended	Tense, straight legs; rigid and/or rapid extension, flexion	
State of Arousal		
0 – Sleeping/Awake	Quiet, peaceful sleeping or alert random leg movement	
1 – Fussy	Alert, restless, and thrashing	

APPENDIX 5

Neonatal Resuscitation within the Birthing Centre Working Protocol

Identification of cases or situations when to call 'NICU'

The goal is to anticipate any identifiable situation that may require neonatal resuscitation team presence prior to the delivery of the newborn in a timely fashion.

The neonatal resuscitation team is composed of neonatologist, respiratory therapist, NICU resuscitation nurse and NICU on call personnel (nurse practitioner, NICU pediatric resident, fellow or clinical assistant) and their spectralink numbers are listed as follows:

Neonatologist- [name]

NICU on call personnel- [name]

Respiratory therapist- [name]

NICU Resuscitation nurse- [name]

*NICU fellow may be called at [name] depending on the availability.

Role within the Birthing Centre

One professional within the birthing center needs to be assigned to each baby to be born. This person needs to be able to initiate resuscitation as per NRP guidelines.

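### Removal pain gets one NIPS total per infant, taken only at removal: prior distress and the two systems cannot be told apart, and the Arms score-1 wording describes legs

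*Combined protocol and SAP*

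**What the plan says.** Aim 2b (Section 2.2) names the outcome: "Pain scale to assess any discomfort or pain during the removal of the sensors". The sentence that introduces the Aim 2 outcomes covers both systems: "The following outcomes will be measured for both wired and wireless systems".

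Section 3.3.4 sets the timing: "neonatal pain will be assessed throughout the sensor removal process", and "The pain scale (NIPS) will be completed by the study team member at the time of sensor removal". It gives the purpose in these words: "At the time of device removal, the researcher will complete the NIPS to ensure removal of adhesive does not cause significant discomfort". It describes NIPS as six items with a range of 0 to 7, where a score above 3 indicates pain.

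In Appendix 1, the pain assessment part of the form is a single block with one score column and one total. It has no pre-removal column and no split between wired and wireless. The vital signs log and the comments log hold no face, cry or arousal score. Muscle tone is the nearest entry.

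On the form, the score-1 descriptor for Arms reads "Tense, straight legs; rigid and/or rapid extension/flexion", the same words as for Legs. Appendix 4 repeats this with a small change of punctuation: "Tense, straight legs; rigid and/or rapid extension, flexion".

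Section 4 gives no analysis of NIPS. Section 5.1 lists pain scores among the data for the lead site's safety reviews after 200 and 400 patients.

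**The concern.** The stated purpose is causal, but one score taken during removal shows only how distressed the infant is at that moment. Cry, facial expression, breathing pattern, limb tension and arousal are not specific to adhesive. Without a score from just before, a high total may reflect removal, a state that was already there, or both.

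The plan accepts this logic for its other scored safety outcome. Skin is photographed before placement and after removal (Section 3.3.4), and skin findings are entered separately for wired and wireless sensors (Appendix 1, part 8). Pain changes faster than skin and has neither safeguard.

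The missing split by system matters as much. Every infant wears both systems (Section 3.3.3). With one total and no removal order, a score cannot be assigned to the investigational sensor or to its comparator. Any carry-over of distress from the first removal to the second also stays hidden.

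The Arms wording is a separate defect of the instrument. The item contradicts itself, and raters at six centers in five countries may resolve the contradiction differently.

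**Working it through.** **1. Reproduce the scale.** Item maxima from the Appendix 1 form: face 1 + cry 2 + breathing 1 + arms 1 + legs 1 + arousal 1 = 7 over six items. This matches the stated range of 0 to 7.

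**2. What prior distress does to the total.** Vigorous cry (2) + fussy (1) = 3, which is not above 3. Four yes/no items remain (face, breathing, arms, legs), giving 2^4 = 16 patterns. Only the pattern with all four at zero stays at 3, so 15 of 16 exceed the cut. Prior distress raises the score in every such infant and crosses the cut once one more item is positive.

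**3. Size, by assumption.** Inputs:
- Planned sample 600 and drop-out 4% (Section 4), so 600 × 0.96 = 576.
- q, the share already above 3 just before removal. The documents do not give it; assumed range 5% to 30%.
- t, the share of the remaining infants whom removal newly pushes above 3. Set to 0 to isolate the artefact.
- Infants above 3 beforehand are assumed to stay above 3 during removal.

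Recorded share above 3 = q + (1 − q)t, which equals q when t = 0.

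| q (assumed) | recorded as in pain, of 576 |
|---|---|
| 5% | 28.8, about 29 |
| 10% | 57.6, about 58 |
| 20% | 115.2, about 115 |
| 30% | 172.8, about 173 |

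At the safety reviews, q = 10% gives 200 × 0.10 = 20 and 400 × 0.10 = 40 such infants.

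**4. Arms wording.** Hold the other four items (face, cry, breathing, arousal) free: 2 × 3 × 2 × 2 = 24 patterns, and call their sum s.
- Only the legs are tense. Correct total s + 1; literal reading s + 2. The total moves from 3 to 4 when s = 2. Patterns with s = 2: cry 0 gives 3, cry 1 gives 3, cry 2 gives 1, so 7 of 24.
- Only the arms are tense. Correct total s + 1; literal reading s. The total moves from 4 to 3 when s = 3. Patterns with s = 3: cry 0 gives 1, cry 1 gives 3, cry 2 gives 3, so 7 of 24.

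The error can therefore create or hide a recorded pain case. These are counts of possible patterns, not frequencies in infants.

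**The case against.** Several points on the other side stand.

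- A reader might infer that the plan counts existing crying and fussing as adhesive pain. The documents do not support that. Those two items reach only 3, and no NIPS analysis rule is written. What can be said is that nothing in the plan separates the two sources.
- A reader might want an inflation factor. With an assumed 2% of new pain among the rest, the recorded rate is 0.10 + 0.90 × 0.02 = 11.8% at q = 10%, and 0.30 + 0.70 × 0.02 = 31.4% at q = 30%. Dividing by 2% gives about 6 to 16. Replacing 2% by 10% gives 19% and 37%, a ratio of only 1.9 to 3.7. The correct divisor would in any case be the cohort effect, (1 − q)t. No such multiple has a source in the documents.
- The plan does not say how the infant is held at removal. The location codes on the form allow kangaroo care, a parent's arms or bed, so distress from being moved cannot be presumed.
- Prior distress inflates recorded pain, which is the cautious direction for safety, and a low rate would still reassure. No stopping threshold rests on NIPS, and the reviews also look at skin lesions and staff surveys. However, this argument does not cover the comparison of systems, where distress left over from the first removal would count against whichever sensor came off second.
- The Arms heading, its neutral score-1 label and its score-0 text all point to arms, so many raters will score it correctly. Appendix 4 presents a cited tool, and whether the wording comes from the source cannot be checked here.
- A site could complete the block twice, or note the infant's state as removal begins. The plan does not ask for either, and the form has room for one total.

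**Conclusion.** The point holds. As planned, Aim 2b cannot separate distress already present from removal pain, and it cannot give a result per system although Aim 2 requires one. Both follow from the text and need no assumption.

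The numerical size is unknown. The range of 29 to 173 infants depends wholly on an assumed 5% to 30% already above 3 who remain there, and it shows scale only. It does not show that pain will be overstated by any given factor or that an interim decision would change.

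The Arms descriptor is a wording error worth one point in either direction. It matters because the cut lies at 3 on a 7-point scale, but how often raters would follow it literally is not known.

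The change is worth making because a score not taken at removal cannot be recovered later.

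**What to change.** 1. Have the researcher record one NIPS immediately before the first sensor is touched.
2. Record one NIPS for the removal of each system, with a short settling score before the second removal.
3. Record the removal order, and alternate or randomise it if practical.
4. Report Aim 2b per system as the change from the preceding score and as new scores above 3 (from 3 or below), alongside the raw scores.
5. Correct the Arms score-1 descriptor on the form and in Appendix 4 so that it describes arms, after checking the source scale and before the form is used further.

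A single baseline with the existing single total would not be enough, because it would still not separate wired from wireless removal. The cost is a few form columns and a minute or two per infant by staff already present. The scorer remains unblinded, and this change does not address that.
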